Appendix F Blood pressure

Blood pressure \leq the 95th percentile for age, height, and gender is required for enrolment. Because measurement accuracy is dependent on the use of proper BP cuff size, BP cuff should be selected as follows:

- Infant 8 to 11 cm.
- Child 12 to 16 cm.
- Small adult 17 to 22 cm.
- Adult 23 to 33 cm.

Age	BP	Systolic blood pressure (mmHg)						Diastolic blood pressure (mmHg)							
(years)	percentile		1	Percen	tile of	heigh	t			1	Percen	tile of	heigh	t	
		5 th	10 th	25 th	50 th	75 th	90 th	95 th	5 th	10 th	25 th	50 th	75 th	90 th	95 th
1	95 th	98	99	101	103	104	106	106	54	54	55	56	57	58	58
2	95 th	101	102	104	106	108	109	110	59	59	60	61	62	63	63
3	95 th	104	105	107	109	110	112	113	63	63	64	65	66	67	67
4	95 th	106	107	109	111	112	114	115	66	67	68	69	70	71	71
5	95 th	108	109	110	112	114	115	116	69	70	71	72	73	74	74
6	95 th	109	110	112	114	115	117	117	72	72	73	74	75	76	76
7	95 th	110	111	113	115	117	118	119	74	74	75	76	77	78	78
8	95 th	111	112	114	116	118	119	120	75	76	77	78	79	79	80
9	95 th	113	114	116	118	119	121	121	76	77	78	79	80	81	81
10	95 th	115	116	117	119	121	122	123	77	78	79	80	81	81	82
11	95 th	117	118	119	121	123	124	125	78	78	79	80	81	82	82
12	95 th	119	120	122	123	125	127	127	78	79	80	81	82	82	83
13	95 th	121	122	124	126	128	129	130	79	79	80	81	82	83	83
14	95 th	124	125	127	128	130	132	132	80	80	81	82	83	84	84
15	95 th	126	127	129	131	133	134	135	81	81	82	83	84	85	85
16	95 th	129	130	132	134	135	137	137	82	83	83	84	85	86	87
≥17	95 th	131	132	134	136	138	139	140	84	85	86	87	87	88	89

Table 26Blood pressure levels for children by age and height percentile –
blood pressure for boys

BP=blood pressure.

Source: National High Blood Pressure Education Program Working Group on High Blood Pressure in Children and Adolescents 2004.

Age	BP		Systolic blood pressure (mmHg)					Diastolic blood pressure (mmHg)							
(years)	percentile			Percer	ntile of	heigh	t		Percentile of height						
		5 th	10 th	25 th	50 th	75 th	90 th	95 th	5 th	10 th	25 th	50 th	75 th	90 th	95 th
1	95 th	100	101	102	104	105	106	107	56	57	57	58	59	59	60
2	95 th	102	103	104	105	107	108	109	61	62	62	63	64	65	65
3	95 th	104	104	105	107	108	109	110	65	66	66	67	68	68	69
4	95 th	105	106	107	108	110	111	112	68	68	69	70	71	71	72
5	95 th	107	107	108	110	111	112	113	70	71	71	72	73	73	74
6	95 th	108	109	110	111	113	114	115	72	72	73	74	74	75	76
7	95 th	110	111	112	113	115	116	116	73	74	74	75	76	76	77
8	95 th	112	112	114	115	116	118	118	75	75	75	76	77	78	78
9	95 th	114	114	115	117	118	119	120	76	76	76	77	78	79	79
10	95 th	116	116	117	119	120	121	122	77	77	77	78	79	80	80
11	95 th	118	118	119	121	122	123	124	78	78	78	79	80	81	81
12	95 th	119	120	121	123	124	125	126	79	79	79	80	81	82	82
13	95 th	121	122	123	124	126	127	128	80	80	80	81	82	83	83
14	95 th	123	123	125	126	127	129	129	81	81	81	82	83	84	84
15	95 th	124	125	126	127	129	130	131	82	82	82	83	84	85	85
16	95 th	125	126	127	128	130	131	132	82	82	83	84	85	85	86
≥17	95 th	125	126	127	129	130	131	132	82	83	83	84	85	85	86

Blood pressure levels for children by age and height percentile - blood Table 27 pressure for girls

BP=blood pressure.

Source: National High Blood Pressure Education Program Working Group on High Blood Pressure in Children and Adolescents 2004.

	Table 28	Canadian	Cardiovascula	r Society	grading of	f angina pe	ectoris
--	----------	----------	---------------	-----------	------------	-------------	---------

Grade	Description
Ι	Ordinary physical activity does not cause angina, such as walking and climbing stairs. Angina with strenuous or rapid or prolonged exertion at work or recreation.
II	Slight limitation of ordinary activity. Walking or climbing stairs rapidly, walking uphill, walking or stair climbing after meals, or in cold, or in wind, or under emotional stress, or only during the few hours after awakening. Walking more than two blocks on the level and climbing more than one flight of ordinary stairs at a normal pace and in normal conditions.
III	Marked limitation of ordinary physical activity. Walking one or two blocks on the level and climbing one flight of stairs in normal conditions and at normal pace.
IV	Inability to carry on any physical activity without discomfort, anginal syndrome may be present at rest.
Source: Ca	ampeau 1976

Source: Campeau 1976.

CONFIDENTIAL AND PROPRIETARY 128 of 183

New York I	Metabolic equivalent ^a	
Class I	No limitations. Ordinary physical activity does not cause undue fatigue, dyspnoea or palpitations (asymptomatic LV dysfunction).	>7
Class II	Slight limitation of physical activity. Ordinary physical activity results in fatigue, palpitation, dyspnoea or angina pectoris (mild CHF).	5
Class III	Marked limitation of physical activity. Less than ordinary physical activity leads to symptoms (moderate CHF).	2 to 3
Class IV	Unable to carry on any physical activity without discomfort. Symptoms of CHF present at rest (severe CHF).	1.6

Table 29New York Heart Association classification

CHF=congestive heart failure; LV=left ventricular; VO₂=maximal oxygen uptake.

^a Metabolic equivalent is defined as the resting VO_2 for a 40-year-old 70 kg man. Metabolic equivalent = 3.5 mL $O_2/min/kg$ body weight.

Appendix G Performance status scales

Table 30Performance status criteria

	Karnofsky (>16 years of age)	Lansky (≤16 years of age)			
Score	Description	Score Description			
100	Normal, no complaints, no evidence of disease.	100	Fully active, normal.		
90	Able to carry on normal activity, minor signs or symptoms of disease.	90	Minor restrictions in physically strenuous activity.		
80	Normal activity with effort; some signs or symptoms of disease.	80	Active, but tires more quickly.		
70	Cares for self, unable to carry on normal activity or do active work.	70	Both greater restriction of and less time spent in play activity.		
60	Requires occasional assistance, but is able to care for most of his/her needs.	60	Up and around, but minimal active play; keeps busy with quieter activities.		
50	Requires considerable assistance and frequent medical care.	50	Gets dressed, but lies around much of the day; no active play, able to participate in all quiet play and activities.		
40	Disabled, requires special care and assistance.	40	Mostly in bed; participates in quiet activities.		
30	Severely disabled, hospitalisation indicated. Death not imminent.	30	In bed; needs assistance even for quiet play.		
20	Very sick, hospitalisation indicated. Death not imminent.	20	Often sleeping; play entirely limited to very passive activities.		
10	Moribund, fatal processes progressing rapidly.	10	No play; does not get out of bed.		

Karnofsky and Lansky performance scores are intended to be multiples of 10.

Appendix H Medications to avoid

Strong or moderate inducers of CYP3A4 as well as strong or moderate inhibitors of CYP3A4 or CYP2C19 are not recommended at any time during the study. During the first cycle concomitant use of strong or moderate inhibitors of CYP3A4 or CYP2C19 should be avoided until after the PK assessment. During the remainder of the study, if concomitant use of selumetinib with strong or moderate CYP3A4 or CYP2C19 inhibitors is not avoidable, then the selumetinib dose should be reduced as shown in Table 31 and the patient should be monitored closely for potential toxicities. The dose of selumetinib should be reduced for the duration of concomitant therapy with the strong or moderate CYP3A4 or CYP3A4 or CYP2C19 inhibitor. After the washout for 5 half-lives of the inhibitor is complete, the selumetinib dose can be re-escalated.

Body Surface	If the current dosaş twice daily, reduce daily (n	ge is up to 25 mg/m ² e to 20 mg/m ² twice ng/dose)	If the current dosage is up to 20 mg/m ² twice daily, reduce to 15 mg/m ² twice daily (mg/dose)		
Area	Morning	Evening	Morning	Evening	
$0.55 - 0.69 \text{ m}^2$	10	10	10 mg o	nce daily	
$0.70 - 0.89 \ m^2$	20	10	10	10	
$0.90 - 1.09 \text{ m}^2$	20	20	20	10	
$1.10 - 1.29 \text{ m}^2$	25	25	25	10	
$1.30 - 1.49 \text{ m}^2$	30	25	25	20	
$1.50 - 1.69 \text{ m}^2$	35	30	25	25	
$1.70 - 1.89 \text{ m}^2$	35	35	30	25	
\geq 1.90 m ²	40	40	30	30	

Table 31Recommended Dosage of Selumetinib for Co-administration with
Strong or Moderate CYP3A4 or CYP2C19 Inhibitors

Note. for patients with BSA 0.55 to 0.69 m^2 , dose reduction is only applicable if the starting dose for this group is 20 mg in the morning and 10 mg in the evening.

Changes to, or addition of medications detailed in Table 32 and Table 33 should be avoided, unless clinically indicated.

Table 32Inhibitors of CYP2C19 or CYP3A4

CYP2C19	СҮРЗА4
fluconazole	Indinavir
fluvoxamine	Nelfinavir
fluoxetine and ticlopidine	Ritonavir
	Clarithromycin

CONFIDENTIAL AND PROPRIETARY 131 of 183

CYP2C19	CYP3A4
	Itraconazole
	Ketoconazole
	Nefazodone
	Saquinavir
	Suboxone
	Telithromycin
	Aprepitant
	Erythromycin
	Fluconazole
	Grapefruit juice
	Verapamil
	Diltiazem

Table 32Inhibitors of CYP2C19 or CYP3A4

Table 33Inducers of CYP3A4

СҮРЗА4
Efavirenz
Nevirapine
Barbiturates
Carbamazepine
Glucocorticoids
Modafinil
Oxcarbazepine
Phenobarbital
Phenytoin
Pioglitazone
Rifabutin
Rifampin
St John's wort
Troglitazone

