6.5 Concomitant therapy

Any medication or vaccine including over-the-counter or prescription medicines, vitamins, and/or herbal supplements that the subject is receiving at the time of enrolment or receives during the study must be recorded along with:

- Reason for use.
- Dates of administration including start and end dates.
- Dosage information including dose and frequency.

Medication/class of drug	Usage (including limits for duration permitted and special situations in which it is allowed)		
Any investigational anticancer therapy other than that under investigation in this study.	Should not be given concomitantly whilst the subject is on study treatment.		

Unless considered to be clinically indicated, subjects should avoid taking other additional nonstudy medications that may interfere with the study medication. Strong or moderate inducers of CYP3A4 as well as strong or moderate inhibitors of CYP3A4 or CYP2C19 are not recommended at any time during the study. During the first cycle concomitant use of strong or moderate inhibitors of CYP3A4 or CYP2C19 should be avoided until after the PK assessment. During the remainder of the study, if concomitant use of selumetinib with strong or moderate CYP3A4 or CYP2C19 inhibitors is not avoidable, then the selumetinib dose should be reduced as shown in Table 31 and the patient should be monitored closely for potential toxicities. The dose of selumetinib should be reduced for the duration of concomitant therapy with the strong or moderate CYP3A4 or CYP2C19 inhibitor. After the washout for 5 half-lives of the inhibitor is complete, the selumetinib dose can be re-escalated. Refer to Appendix H for more detail.

Selumetinib capsules contain vitamin E in the form of D- α -tocopheryl polyethylene glycol 1000 succinate, a water-soluble form of vitamin E which acts as a formulation excipient. The maximum daily dose of vitamin E that a study subject may receive from selumetinib is approximately 261.6 mg/day. Therefore, subjects should not take any supplemental vitamin E. High doses of vitamin E have been reported to cause bleeding and interfere with blood coagulation processes.

Selumetinib should be administered with caution in subjects who are also receiving concomitant coumarin anticoagulant medications (e.g. warfarin). These subjects should have their international normalised ratio monitored/anticoagulant assessments conducted more frequently and the dose of the anticoagulant should be adjusted accordingly.

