Prohibited medication/class of drug	Usage (including limits for duration permitted and special situations in which it is allowed)
Other IMP	Not allowed for 4 weeks or 5 half-lives (whichever is more appropriate as judged by the investigator) prior to the first dose of study treatment.
MEK, Ras or Raf inhibitor	Prior treatment is prohibited.
Other systemic PN target treatment (including chemotherapy, hormonal therapy, radiation therapy, immunotherapy or biologic therapy)	Not allowed for 4 weeks or 5 half-lives (whichever is more appropriate as judged by the investigator) prior to the first dose of study treatment.
Multivitamins containing vitamin E	Must be stopped prior to initiation of selumetinib.
Herbal supplements or medications known to be strong or moderate inducers of CYP3A4, or strong or moderate inhibitors of CYP3A4 and CYP2C19 (Appendix H)	Must be safely discontinued at least 14 days before the first dose of study medication. Strong or moderate inducers of CYP3A4 are not allowed at any time during the study.
	Concomitant use of strong or moderate inhibitors of CYP3A4 and CYP2C19 should be avoided until after the PK assessment on Cycle 1 Day 8. During the remainder of the study (i.e. from Cycle 1 Day 9 onwards), if concomitant use of strong or moderate CYP3A4 and CYP2C19 inhibitors is not avoidable, then the selumetinib dose should be reduced as shown in Appendix H.

Table 6Prohibited medications

CYP=cytochrome P450; IMP=investigational medicinal product; MEK=mitogen activated protein kinase kinase.

Pain medication usage will be analysed separately (see Section 8.1.3.1.5).

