6.6 Dose modification and discontinuation

Specific guidance for the management of AEs, including interruption or reduction of treatment with selumetinib, may be considered for particular events of special interest (i.e. diarrhoea, dyspnoea, rash, asymptomatic reduction in LVEF, and visual disturbance), as indicated in the algorithms provided in Appendix E. Oral care recommendations are also provided in Appendix E. Some AEs (hyperphosphatemia and increase in calcium phosphate) should be managed according to local practice.

For all AEs reported in this study that are considered at least partly related to administration of selumetinib, the following dose reduction/adjustment guidance should be applied unless otherwise specified in the Guidance for management of specific AE (Appendix E):

- Treatment with selumetinib should be temporarily interrupted if one of the following AEs occurs and is considered related to treatment with selumetinib:
 - Any intolerable AE regardless of grade.
 - Any AE CTCAE grade 3.

On improvement of the AE to CTCAE grade 1 or less within 4 weeks of onset, study treatment may be restarted at a reduced dose at the discretion of the investigator. Twostep dose modification is applied in the study (see Table 7). Any subjects with 2 prior dose reductions who experience a toxicity that would cause a third dose reduction must be discontinued from study treatment.

Body surface area (m ²)	Selumetinib dose (mg) ^a Dose level 0		First selumetinib dose (mg) reduction		Second selumetinib dose (mg) reduction ^b	
	AM	PM	AM	PM	AM	PM
0.55 to 0.69	20	10	10	10	10 mg once daily	
0.7 to 0.89	20	20	20	10	10	10
0.9 to 1.09	25	25	25	10	10	10
1.1 to 1.29	30	30	25	20	20	10
1.3 to 1.49	35	35	25	25	25	10
1.5 to 1.69	40	40	30	30	25	20
1.7 to 1.89	45	45	35	30	25	20
≥1.9	50	50	35	35	25	25

Table 7Two-step Dose Modification Procedure

- ^a Actual dose in mg (capsule sizes 10 and 25 mg) administered every 12 hours to achieve a dosage of 25 mg/m² twice daily.
- ^b Permanently discontinue selumetinib in patients unable to tolerate Selumetinib after two dose reductions.
- If a different AE subsequently requires dose interruption, appropriate selumetinib dose modification should be considered on improvement of the AE at the discretion of the investigator, in line with Table 7.
- The dose may be increased to account for an increase in BSA at the time of on study evaluations.

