7.1.1 Temporary discontinuation

Dosing can be interrupted due to AEs or unforeseen circumstances as described in Section 6.6.

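### Table 31 offers no lower dose for a subject already at the second Table 7 reduction, so the instruction to reduce for an unavoidable CYP inhibitor cannot be met at that level

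*Protocol*

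**What the plan says.** Protocol Section 6.5 and Appendix H discourage strong or moderate CYP3A4 or CYP2C19 inhibitors throughout. If one is unavoidable after the pharmacokinetic assessment in Cycle 1, "then the selumetinib dose should be reduced as shown in Table 31 and the patient should be monitored closely for potential toxicities". Section 6.5 adds: "The dose of selumetinib should be reduced for the duration of concomitant therapy with the strong or moderate CYP3A4 or CYP2C19 inhibitor". Table 6 repeats the rule by pointing to the appendix: "then the selumetinib dose should be reduced as shown in Appendix H". Once the inhibitor has gone, "After the washout for 5 half-lives of the inhibitor is complete, the selumetinib dose can be re-escalated".

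Table 31 has two columns. The left is for a current dosage of up to 25 mg/m² twice daily and aims at 20 mg/m². The right is headed "If the current dosage is up to 20" mg/m² twice daily and aims at 15 mg/m². A note covers the smallest BSA band only: "dose reduction is only applicable if the starting dose for this group is 20 mg in the morning and 10 mg in the evening".

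Table 7 in Section 6.6 allows two dose reductions for toxicity, with treatment continuing at the second level. Below that level the protocol gives no dose: "Any subjects with 2 prior dose reductions who experience a toxicity that would cause a third dose reduction must be discontinued from study treatment". Section 7.1.1 says: "Dosing can be interrupted due to AEs or unforeseen circumstances as described in Section 6.6". Section 7.1 also allows treatment to be stopped when that is judged best for the patient, with the sponsor notified.

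**The concern.** The co-medication rule makes no exception for a subject whose dose has already been lowered. Table 31 looks built for two starting points, full dose and one reduction, while Table 7 has three levels at which a subject can be on treatment. If the third level has no lower entry, a site with such a subject has no listed dose to give.

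The subjects concerned have already shown poor tolerance twice, and the inhibitor is a reason to give less drug. Sites could respond differently: keep the dose, interrupt, stop, or read off the BSA row and give what it shows. Safety and tolerability are primary objectives, and half of the planned subjects are children, so a dosing rule that fails at one level deserves a correction even if it is rarely reached.

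**Working it through.** **Inputs.** Morning plus evening dose in mg/day, by BSA band, from Table 7 (Section 6.6) and Table 31 (Appendix H).

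| BSA (m²) | Level 0 | First reduction | Second reduction | Table 31 left | Table 31 right |
|---|---|---|---|---|---|
| 0.55–0.69 | 30 | 20 | 10 | 20 | 10 |
| 0.70–0.89 | 40 | 30 | 20 | 30 | 20 |
| 0.90–1.09 | 50 | 35 | 20 | 40 | 30 |
| 1.10–1.29 | 60 | 45 | 30 | 50 | 35 |
| 1.30–1.49 | 70 | 50 | 35 | 55 | 45 |
| 1.50–1.69 | 80 | 60 | 45 | 65 | 50 |
| 1.70–1.89 | 90 | 65 | 45 | 70 | 55 |
| ≥1.90 | 100 | 70 | 50 | 80 | 60 |

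**Step 1: does the table work where it should?** Change = Table 31 entry minus current dose, in mg/day, bands in ascending order.

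- Level 0 to left column: −10, −10, −10, −10, −15, −15, −20, −20. Lower in 8 of 8.
- First reduction to right column: −10, −10, −5, −10, −5, −10, −10, −10. Lower in 8 of 8.

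**Step 2: the second reduction.**

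- To right column: 0, 0, +10, +5, +10, +5, +10, +10. As a percentage of the current dose: 0, 0, 10/20 = 50%, 5/30 = 17%, 10/35 = 29%, 5/45 = 11%, 10/45 = 22%, 10/50 = 20%.
- To left column: +10, +10, +20, +20, +20, +20, +25, +30.

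None of the 16 cells (8 bands × 2 columns) is lower. Taking morning and evening doses separately changes nothing: no single entry in either column is below the corresponding second-reduction dose.

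**Step 3: does the right-hand column cover these subjects?** Average dose per 12 hours = (daily mg ÷ 2) ÷ BSA, at the lower and upper limit of each band: 9.1–7.2, 14.3–11.2, 11.1–9.2, 13.6–11.6, 13.5–11.7, 15.0–13.3, 13.2–11.9, and 13.2 mg/m² at 1.90 m². All are below 20 mg/m², so the header includes them, and all are already at or below the 15 mg/m² target. One qualification applies: in the smallest band the second reduction is 10 mg once daily, which a header written for twice-daily dosing does not strictly cover.

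**Step 4: is the column to use stated by dose level?** It is not. The headers are in mg/m², and they overlap. At the first reduction the same formula gives 30 ÷ 2 ÷ 0.70 = 21.4 mg/m² and 45 ÷ 2 ÷ 1.10 = 20.5 mg/m² at the bottom of two bands, which is above 20. Reading those subjects into the left column would give no change (30 versus 30 mg/day) or an increase (50 versus 45 mg/day). The mapping that works in Step 1 therefore has to be inferred.

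**Step 5: does another rule settle the case?** The two stopping rules in Section 6.6 need a further toxicity or intolerance; starting an inhibitor is neither. The Table 31 note concerns one band and turns on the starting dose, which in this protocol is always 20 mg and 10 mg in that band (Table 4). Section 7.1.1 names unforeseen circumstances but refers to Section 6.6, which describes interruption for adverse events only. Discontinuation in the patient's interest is a general provision. None of them says what dose to give.

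**The case against.** The strongest reply is that nothing in the protocol tells a site to give more drug. A reader might infer from the six higher entries that the protocol orders an increase. The documents do not support that: the text speaks of reducing, the column headers do too, and re-escalation is reserved for after inhibitor washout. A clinician who reads the sentence as well as the table would not raise the dose. This stands, and the point is therefore an instruction that cannot be met, with a lookup that errs if followed literally.

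A reader might also infer that sites are left with no way out. That goes too far. Section 7.1.1 does mention unforeseen circumstances, and Section 7.1 allows stopping in the patient's interest. Section 6.6 requires interruption for intolerable or grade 3 related events, and discontinuation if a third reduction would be needed. Harm that does appear is covered. What is missing is the step before harm appears.

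A third tempting inference is that selumetinib should be interrupted by default. The protocol gives no figure for the inhibitor's effect on exposure, and these subjects already average no more than 15 mg/m² per 12 hours. Holding the dose with close monitoring is a defensible reading of the same sentence. A mandatory interruption could also withhold treatment for as long as a long-term inhibitor is needed.

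Finally, the case is uncommon. It takes two toxicity reductions, continued treatment and an unavoidable inhibitor from a class that the protocol discourages. Pharmacokinetic sampling ends on Cycle 1 Day 8, and inhibitors are to be avoided until then, so the planned pharmacokinetic analysis is not at stake.

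**Conclusion.** The gap is real and narrow. Table 31 fits dose level 0 and the first reduction and fails at the second, where no entry is lower than the current dose: the right-hand column is equal in two BSA bands and 5 to 10 mg/day (11% to 50%) higher in six. This is a stated lookup rule that returns an unsuitable dose for subjects whom its header covers, so it is more than missing detail.

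The arithmetic rests only on the doses printed in Tables 7 and 31. That few subjects will be affected is a judgement from the conditions required and the planned size of about 32; the protocol gives no rate for second reductions or inhibitor use. Whether these subjects need a lower dose, the same dose or a pause cannot be decided from the document. The conclusion is limited to this: the table must not be applied as it stands at that level, and the protocol should say so.

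**What to change.** Add one note to Table 31, with a cross-reference in Section 6.5 and in Table 6:

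1. The left column applies to subjects at dose level 0, and the right column to subjects at the first Table 7 reduction.
2. A Table 31 entry equal to or above the subject's current dose must never be applied.
3. For a subject at the second reduction who needs an unavoidable strong or moderate inhibitor, the dose must not be increased. Whether to hold the dose with close monitoring, interrupt or discontinue is agreed with the study physician.

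The first two items follow from the protocol's own tables. The third leaves the clinical choice open and does not mandate interruption. The cost is one table note, two cross-references and a contact with the study physician in the rare affected case; no visits, tests or samples are added.
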